#### **7.2.6. Urine Pregnancy tests**

At Visits 2, and 5-11, a qualified staff member will perform a urine pregnancy test for subjects who are WOCBP. The urine pregnancy test kits used must have a minimum sensitivity of 25-mIU  $\beta$ -HCG/milliliter (ml) of urine.

Subjects who are WOCBP must have a negative serum pregnancy test result at Visit 1 to continue in the study and a negative urine pregnancy test at Visit 2 to be continue in the study and apply study medication.

If the result of any urine pregnancy test is positive following initial study medication application, the subject will be withdrawn from the study and the subject's pregnancy documented and followed.

### **7.3. Other Evaluations**

#### **7.3.1. Demographics, medical history and alopecia areata history**

During Visit 1, the investigator or designee will interview each subject to obtain demographic information including date of birth, sex at birth, Fitzpatrick skin type, race and ethnicity.

The investigator or designee will interview each subject to obtain medical history information related to all medical conditions and disease states that, at Visit 1: are ongoing, require concomitant therapy or are, in the opinion of the investigator, relevant to the subject's study participation. The investigator or designee will also obtain an AA, AU or AT history at Visit 1. In addition, the medical history of women who are not of childbearing potential should reflect the reason e.g. post-menopausal for 1 year or greater, bilateral tubal ligation, or hysterectomy.

### **7.3.2. Standardized photography**

At Visits 2 and 5-11 a qualified investigational center staff member will take standardized color photographs of each subject's eyebrows.

The photographs are to document the status of each subject's eyebrows. The subject's identity will not be revealed in the study photographs.

At Visit 2, the photographs must be taken prior to the first study medication application.

Equipment, supplies, training and detailed instructions for obtaining and managing the photographs will be provided to the investigational center prior to the initiation of subject enrollment.

## **8. ADVERSE EVENTS**

Adverse events will be monitored throughout the study and immediately reported on the appropriate Aclaris Therapeutics, Inc. AE eCRF.

### **8.1. Definitions**

#### **8.1.1. Adverse events (AE)**

An AE is any untoward medical occurrence in a patient or clinical investigation subject administered a study medication and which does not necessarily have a causal relationship with the study medication. An AE can therefore be any unfavorable and unintended sign or symptom associated with the use of a study medication (including an abnormal laboratory finding), whether or not related to the study medication. Thus, any new, or clinically significant worsening of an existing sign, symptom or disease, should be considered an AE.

**Worsening of any of the eyebrow assessments should be reported as an AE ONLY if the use of the study medication is interrupted or discontinued or if therapy is required to manage the event.**

**The investigator must, for any AE in a study medication treatment area, question the subject in detail to determine if there are any confounding factors (e.g., irritation by cosmetics) for any such AE.**

CONFIDENTIAL  
Page 42 of 57

Every new episode or clinically significant worsening of a chronic condition (e.g., headaches, seasonal allergies, depression, and hypertension) should be reported as a separate AE, even if the condition is reported in the subject's medical history.

The investigator should, when certain, report a diagnosis rather than the signs, symptoms or clinically significant abnormal laboratory values associated with the AE. Otherwise, signs, symptoms or abnormal laboratory values may be used to describe the AE.

Any CS abnormality discovered prior to the first study medication application should be reported as medical history, not as an AE.

### **8.1.2. Serious adverse event (SAE)**

A Serious Adverse Event is any untoward medical occurrence that at any dose:

- Results in death
- Is life threatening
- Requires inpatient hospitalization or prolongation of existing hospitalization
- Results in persistent or significant disability/incapacity, or
- Is a congenital anomaly/birth defect
- Is an important medical event

The term "life threatening" refers to an event in which the subject was at risk of death at the time of event; it does not refer to an event that hypothetically might have caused death if it was more severe.

Inpatient hospitalization is considered to have occurred if the subject is admitted to the hospital on an in-patient basis, even if released the same day. Prolongation of hospitalization is defined as an additional night stay in the hospital. Hospitalization for a diagnostic test (even if related to an AE) or elective hospitalization that was planned before study enrollment (signing the ICF) are not themselves reasons for an event to be defined as a SAE.

Important medical events are those that may not be immediately life threatening, result in death or hospitalization, but are clearly of major clinical significance and may jeopardize the subject or require intervention to prevent one of the outcomes listed in the SAE definition above. These should also usually be considered serious. Examples of such events are intensive treatment in an emergency room or at home for allergic bronchospasm, blood dyscrasias or convulsions that do not result in hospitalization.

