### **8.1.3. Adverse event reporting period**

The investigator must start reporting non-serious AEs and SAEs starting with the subject's first study medication application continuing until the end of the subject's last study visit.

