### 8.2. Reporting Procedures

#### 8.2.1. Procedures for reporting adverse events

At each post randomization visit (Visit 2), the investigator or designee will question the subject to elicit AEs using a non-directive question such as “Has there been any change in your health since the previous study visit?”

At Visit 2, the investigator or designee will monitor the subject for at least 20 minutes after the first study medication application at Visit 2 to elicit AEs in a similar manner.

If appropriate, based on the subject's response to non-directed questioning regarding AEs, the investigator or designee will follow-up with directed questions and appropriate evaluations.

Any AE noted during the reporting period must be reported in the source documents and on the appropriate AE eCRF.

AEs that are defined as “Not Related” to the study medications will be followed until they are resolved or until the subject’s last study visit. AEs that are defined as “Related” to the study medications will be followed until they are resolved or, if not resolved after the subject’s last study visit, until in the opinion of the investigator, the AE reaches a clinically stable outcome with or without sequelae.

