### **8.2.3. Safety Monitoring ECG Discontinuation Criteria**

Any subject who develops any of the following ECG criteria during the active treatment phase will be instructed to stop study medication and will be withdrawn from the study:

- A post-study medication ECG result where the evaluator’s interpretation shows any of the following:
  - Clinically significant rhythm disturbance other than sinus rhythm or ectopic supraventricular rhythm (ectopic atrial rhythm)
  - Clinically significant conduction disturbance including PR >240msec, pre-excitation (delta wave and PR <120msec), second degree or higher AV block

CONFIDENTIAL  
Page 45 of 57

- New finding of QRS>120ms (if not present at screen. For example, subjects with Right Bundle Branch Block at screening would not need to be withdrawn from the study if their subsequent ECGs remained unchanged)
- Evidence of QT-interval prolongation, defined as an increase in the QTcF interval >60ms from Visit 1
- New QTcF > 500 ms
- Acute signs of ischemia or infarction
- Any ECG abnormality which may, in the opinion of the investigator, represent a new medical issue of concern

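### Section 8.1.2 allows an on-study adverse event whose only serious feature is an unplanned inpatient diagnostic admission to be classed as non-serious

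*Combined protocol and SAP*

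**What the plan says.** Section 8.1.2 lists the criteria that make an untoward occurrence serious. One is that it "Requires inpatient hospitalization or prolongation of existing hospitalization". A later paragraph defines that criterion: inpatient hospitalization has occurred once the subject is "admitted to the hospital on an in-patient basis, even if released the same day". The purpose of the admission plays no part in the definition.

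The same paragraph then sets out two exemptions. The first is "Hospitalization for a diagnostic test (even if related to an AE". The second is "elective hospitalization that was planned before study enrollment (signing the ICF". Of both it says that they "are not themselves reasons for an event to be defined as a SAE".

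Section 8.1.3 fixes the reporting period for AEs and SAEs as "starting with the subject's first study medication application continuing until the end of the subject's last study visit". Section 8.2.2 sets the duties that attach to an SAE. Section 8.2.1 covers the follow-up of AEs in general.

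**The concern.** The two exemptions differ in kind. An elective admission arranged before consent was not caused by anything that happened on study, so leaving it out of the SAE count is sensible. An admission to investigate an AE is different, because the AE is the reason the subject is in hospital. The wording in parentheses brings that second kind of admission into the exemption explicitly.

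What is at stake is expedited safety reporting. Safety is part of the main objective (Section 4), and Section 10.2 describes this as the first US-based study of the topical solution for eyebrow loss in this disease. Whether an event is called serious decides whether the Section 8.2.2 procedure starts at all. Section 8.1.2 also gives no rule for an admission that combines tests with observation or treatment, so two investigators could classify the same case differently.

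**Working it through.** No arithmetic applies: the protocol ties no figure to this definition. The check sets the sentences side by side and runs one test case through them.

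**Test case.** A subject on treatment develops an AE, is admitted as an inpatient for a diagnostic test that nobody had planned, is discharged, and meets no other seriousness criterion.

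1. *Criterion.* Under the hospitalization bullet and its definition in 8.1.2, the event is serious, because an inpatient admission took place and its length and purpose do not matter.
2. *Exemption.* Under the diagnostic-test clause, that admission is not in itself a reason to call the event an SAE. The admission was the only reason, so the event becomes non-serious.
3. *Does the condition of planning before consent also limit the diagnostic-test clause?* Grammatically it follows elective hospitalization. In substance it cannot sensibly reach further back. Section 8.1.1 ties an AE to a subject given study medication and sends abnormalities found before the first application to medical history. Section 8.1.3 starts AE reporting at the first application. A test related to an AE would therefore not normally have been arranged before the ICF was signed. The clause reaches unplanned, on-study admissions, and no other section narrows it.
4. *Other criteria.* The exemption says only that the admission is not itself a reason, so death, threat to life, disability, congenital anomaly and important medical event all remain. In the test case only the last could apply. It is a matter of judgment, and 8.1.2 says such events should usually, not always, be considered serious.
5. *Consequence of the classification.*

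| | Classed as SAE (8.2.2) | Classed as non-serious |
|---|---|---|
| Safety Monitor | Immediate email, whatever the causality | No such notice |
| Forms | AE eCRF and SAE form within 24 hours | AE eCRF (Section 8) |
| Follow-up | To resolution or a stable outcome, with the investigator and the sponsor's Safety and Medical Monitors agreeing that it is satisfactorily resolved | Related: to resolution or a stable outcome in the investigator's opinion. Not Related: "to the study medications will be followed until they are resolved or until the subject" reaches the last visit (8.2.1) |
| Monthly safety review (7.2) | Yes | Yes |

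The event stays in the AE data either way. What it loses is the first three entries in the SAE column.

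**The case against.** The strongest reply is that 8.1.2 states a general rule followed by an express exception, which is a normal way to draft. A reader might infer that the section contradicts itself and that a site cannot follow both sentences. The text does not support that: a site applies the rule and then the exception, and gets an answer. The objection stands on this point. The problem is what the exception lets through.

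The exception is also narrower than it first looks. It covers admission for a test, and does not mention admission for treatment or monitoring. An overnight stay for chest pain or a suspected severe infection would often involve more than a test. The important-medical-event paragraph names blood dyscrasias among its examples, so some cytopenias have a route back to SAE status. This too stands, and it confines the point to events whose only serious feature is a purely diagnostic admission.

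A reader might further infer that the gap falls mainly on the events the protocol worries about most: ECG changes, cytopenias and liver enzyme rises. The documents do not support that either, because many of those events reach the sponsor by another path:

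- Listed ECG findings during active treatment, a list that ends with "Any ECG abnormality which may, in the opinion of the investigator, represent a new medical issue of concern", lead to withdrawal (8.2.3), and discontinuation is notified to the sponsor's study monitor within 24 hours (5.6).
- Dose interruptions for Table 1 laboratory values must be notified to the Medical Monitor (8.2.4.1).
- Continued treatment after other serious or severe related AEs should be discussed with the medical monitor (8.2.4.2).
- Related AEs are followed to resolution or a stable outcome even when non-serious (8.2.1).
- An independent safety monitor reviews the data at least monthly (7.2).

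These safeguards reduce the harm but do not remove it. Monthly review is not immediate notice. The ECG and Table 1 routes depend on a listed finding and on stopping or interrupting treatment. They do not reach an AE of another kind, or one arising in the four-week no-treatment follow-up, which is still inside the reporting period.

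**Conclusion.** The point holds in a limited form. Followed as written, 8.1.2 allows an AE-prompted, unplanned inpatient admission for a diagnostic test to be recorded as non-serious when the event has no other serious feature and the investigator does not use the important-medical-event criterion. Such an event misses the Safety Monitor notice, the 24-hour SAE form and the joint agreement on resolution.

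The size cannot be put as a rate. With about 12 subjects, a reader might infer that one reclassified admission would visibly move the study's SAE rate. That presupposes the event happens, and the documents give no expected frequency of diagnostic admissions; the oral Phase 1 study summarized in Section 3.1 had no SAEs. Section 10.1 plans proportions of subjects with treatment-emergent AEs by System Organ Class and names no SAE-rate output, and the event would still count there. No endpoint, estimate or analysis population changes.

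The conclusion rests on two readings: that the condition of planning before consent does not limit the diagnostic-test clause, and that no site instruction outside these documents narrows it. The change is worth making because it is cheap and concerns safety reporting. It is not a flaw that threatens the study.

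**What to change.** Reconcile the sentences in Section 8.1.2 in one of two ways:

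- limit the diagnostic-test exemption to admissions that were not prompted by an AE; or
- delete the diagnostic-test part of the sentence, including its parenthesis, so that only elective admissions planned before the ICF remain exempt.

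Either way, keep the exemption for planned elective admissions. Any inpatient admission prompted by an AE would then meet the hospitalization criterion directly, and admissions that mix work-up with treatment would need no separate rule.

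The cost is one sentence in the protocol and a matching line in the SAE training material. The downside is that a few brief work-up admissions will be reported as SAEs, a small burden among about 12 subjects.

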### **8.1.3. Adverse event reporting period**

The investigator must start reporting non-serious AEs and SAEs starting with the subject's first study medication application continuing until the end of the subject's last study visit.

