## **5.6. Subject Discontinuation from the Study**

Subjects will be informed that they are free to withdraw from the study at any time and for any reason. The Investigator may remove a subject from the study if, in the Investigator's opinion, it is not in the best interest of the subject to continue the study. Examples of other reasons subjects may be discontinued from the study are: a change in compliance with an inclusion or exclusion criterion, occurrence of AEs, occurrence of pregnancy, or use of a prohibited therapy. Notification of discontinuation will immediately (within 24 hours) be made to the Aclaris Therapeutics, Inc. study monitor.

In case of premature discontinuation of study participation, efforts will be made to perform all final study day assessments. The date the subject is withdrawn from the study and the reason for discontinuation will be recorded in the subject's source documents and on his/her case report forms (eCRFs). All withdrawn subjects with ongoing AEs will be followed as specified in section 8.2.1 of this protocol.

The study may be discontinued at the discretion of Aclaris Therapeutics, Inc. Some examples of reasons for discontinuation are the occurrence of the following:

- Increased frequency, severity or duration of known AEs
- Medical, business, regulatory or ethical reasons affecting the continued performance of the study
- Difficulties in the recruitment of subjects

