#### **6.3.5. Visit 11 (Week 28)**

This visit must occur 28 weeks ( $\pm 4$  days) after Visit 2.

At this visit, the investigator or designee will perform the following procedures:

1. Query the subject in a non-directive manner about any changes in her/his health since the previous visit and report all AEs on the appropriate form.
2. Query the subject about any changes in her/his concomitant therapies since the previous visit and report changes on the appropriate form.
3. Confirm the subject continues to comply with all study restrictions and has followed all study instructions.

4. Conduct a brief physical examination.
5. Measure vital signs.
6. Conduct an ECG.
7. Confirm subject had clinical laboratory tests prior to visit (same day).
8. Perform a urine pregnancy test for WOCBP.
9. Have the subject perform a LTA.
10. The investigator or designee will perform a LTA.
11. The investigator or designee will perform the CEA.
12. Have the subject complete the SEA.
13. Have the subject complete the SES.
14. Take standardized photographs.
15. Discharge the subject from the study.

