#### 7.2.1. ECGs

At Visits 1, 2, 10 and 11 a standard 12-lead ECG will be performed by a qualified staff member. The ECGs must be obtained using a standard 12-lead ECG with a 10mm/mV amplitude, at 25mm/sec and a 5-10-second duration. To ensure a steady heart rate the subject must rest quietly in the supine position for at least 5 minutes prior to performing the ECG.

A central lab will provide equipment, supplies and site training. In addition, the central lab will process the ECGs received by the sites and report results via a secure study portal. The ECG results will be interpreted by a qualified health professional (evaluator) and the interpretation reported either directly on the tracing or in a separate report. The evaluator will interpret the results of every ECG and define the ECG as “normal” or “abnormal”. Variations such as minor ST changes (*i.e.*, <0.5mm depression) and early re-polarization are considered normal.

The investigator must review the evaluator’s interpretation of each subject’s Visit 1 ECG prior to Visit 2. The investigator will review the evaluator’s interpretation of all ECG reports in a timely manner and comment on the clinical significance of any result that is defined by the evaluator as abnormal.

Any abnormalities that are, in the opinion of the investigator, CS must be reported as medical history if found prior to the start of the first study medication application or as an AE if found after the start of the first study medication application.

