### **8.2.2. Procedure for reporting a serious adverse event**

Upon becoming aware of a SAE occurring during the AE reporting period, whether or not related to the study medication, the investigator must:

1. Take the appropriate medical action to ensure the subject’s safety.
2. Immediately inform the Safety Monitor of the SAE by email, ensuring that the subject information is deidentified (only subject initials and subject number) to:
  - **ProPharma, Email:** [[contact]](mailto:[contact])
  - **[contact]**
3. Print a copy of the email confirmation from ProPharma and place in the study file.
4. Within 24-hours complete, as fully as possible, an AE eCRF and an SAE form; e-mail the forms and any other relevant information (e.g., concomitant medication eCRF, medical history eCRF, laboratory test results) to ProPharma (Aclaris Therapeutics, Inc. Safety Monitor).
5. Monitor and document the progress of the SAE until it resolves or, if not resolved after the subject’s last study visit, until in the opinion of the investigator the AE reaches a clinically stable outcome with or without sequelae AND the investigator and Aclaris Therapeutics, Inc. Safety and Medical Monitor agree that the SAE is satisfactorily resolved.
6. Inform the Aclaris Therapeutics, Inc. Safety Monitor of SAE updates, via telephone, followed by an SAE form update sent by e-mail.
7. Comply with the appropriate regulatory requirements and Aclaris Therapeutics, Inc. instructions regarding reporting of the SAE to the responsible Institutional Review Board (IRB) or Ethics Committee (EC).

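### Subjects who leave the study when drug stops can have no off-drug AE reporting time, against a planned 28 days for completers, and the rule for Visit 11 results read after discharge is inconsistent

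*Combined protocol and SAP*

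**What the plan says.** Section 8.1.3 runs AE and SAE reporting from the first application, "continuing until the end of the subject's last study visit". Section 8.2.1 adds: "Any AE noted during the reporting period must be reported in the source documents and on the appropriate AE eCRF". The SAE duty in Section 8.2.2 begins "Upon becoming aware of a SAE occurring during the AE reporting period, whether or not related to the study medication".

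For completers, treatment ends at Visit 10 (Day 169). Visit 11 (Day 197) follows, with an AE query, physical examination, vital signs, laboratory tests and ECG (Section 6.3.5).

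For subjects who leave early, Section 5.6 says: "In case of premature discontinuation of study participation, efforts will be made to perform all final study day assessments". It gives no timing relative to the last application and no later contact. It refers ongoing AEs to Section 8.2.1, which follows unrelated AEs no further than the last visit and related AEs until they resolve or stabilise.

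Three sections remove a subject from the study, not only from drug: 6.6.8 (twice-daily application not possible for more than 4 consecutive days), 7.2.6 (positive pregnancy test after first application) and 8.2.3 (ECG criteria). Section 8.2.4.2 lists reasons to discontinue drug permanently but does not say whether those subjects stay in the study.

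On final results, Visit 11 bloods are drawn the same day, "the central lab will process the ECGs received by the sites and report results via a secure study portal" (Section 7.2.1), and the last step of the visit is "Discharge the subject from the study". No turnaround time is stated. Sections 7.2.1 and 7.2.4 make clinically significant ECG and laboratory findings AEs if found after the first application, with no end date.

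**The concern.** The reporting window is tied to a visit, not to the last application. For completers this makes little difference, because the visit is placed about 4 weeks after drug stops. For a subject withdrawn on the day drug stops, the window can close that same day. Some of the routes out are safety routes, so a subject with a safety signal may be observed for the shortest time off drug.

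Safety and tolerability are part of the main objective (Section 4). Section 10.1 reports the proportion of subjects with treatment-emergent AEs, does not say when treatment emergence ends, and makes no allowance for unequal collection time. Subjects who leave are not replaced (Section 5.8).

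There is a second, smaller problem. The Visit 11 laboratory tests and ECG are the only ones planned off drug, and two sets of rules give different answers on whether a finding read after discharge must be reported.

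**Working it through.** **1. Off-drug time inside the window, completers.** Inputs: Visit 10 on Day 169 and Visit 11 on Day 197 (Section 6.2), each ±4 days and both counted from Visit 2 (Sections 6.3.4 and 6.3.5).

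- Planned: 197 − 169 = 28 days, which reproduces the protocol's stated 28-day no-treatment period.
- Shortest: (197 − 4) − (169 + 4) = 193 − 173 = 20 days.
- Longest: (197 + 4) − (169 − 4) = 201 − 165 = 36 days.

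**2. Off-drug time inside the window, early leavers.** Section 5.6 sets no interval between last application and last visit, so the guaranteed minimum is 0 days.

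**3. What each rule covers.**

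| Situation | Result under the text |
|---|---|
| Completer, new AE 10 days after last application | Before Visit 11 even at the 20-day minimum: reportable |
| Subject whose last visit is the day drug stops, new non-serious AE 10 days later | Outside 8.1.3; 5.6 covers ongoing AEs only: not reportable |
| Same subject, new SAE 10 days later | 8.2.2 requires occurrence within the period: not reportable |
| Same subject, related AE or any SAE ongoing at last visit | Followed to resolution or stability (8.2.1, 8.2.2) |
| Same subject, unrelated non-serious AE ongoing at last visit | Follow-up ends at that visit (8.2.1) |
| Visit 11 laboratory or ECG finding, clinically significant, read after discharge | AE under 7.2.1 or 7.2.4; not clearly within the duty in 8.2.1 |

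**4. Weight of one event.** 1/12 = 8.3 percentage points.

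**5. How many subjects?** The documents give no dropout rate, so the following rates are assumptions. With rate d among 12 subjects, the expected number is 12d and the chance of at least one early leaver is 1 − (1 − d)^12.

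- d = 10%: 1.2 subjects; 72%.
- d = 20%: 2.4 subjects; 93%.
- d = 30%: 3.6 subjects; 99%.

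Planned off-drug observation is 12 × 28 = 336 subject-days. Each early leaver with 0 off-drug days removes 28 of them, or 28/336 = 8.3%. An assumed 1 to 4 such subjects gives 8% to 33%. These are maxima, and they count days, not events.

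**The case against.** The strongest reply is that most of the safety information is already secured. Completers have a full off-drug visit inside the window. The event that causes a safety withdrawal occurs within the window and, if related or serious, is followed past the last visit. Pregnancies have their own reporting and follow-up route (Section 9.2). The reported half-life of about 9.0 hours makes five half-lives 45 hours, or 1.9 days, so lingering exposure is short. The study is small, single-arm and descriptive, with no between-arm comparison to bias. All of this stands and limits the point to new events after early withdrawal. It does not close the gap: even 1.9 days are not guaranteed, the half-life comes from oral dosing of the prodrug, and 4 weeks is the protocol's own choice for completers.

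It can also be said that Section 8.2.3 will seldom produce an early leaver. Scheduled ECGs are at Visits 1, 2, 10 and 11, and the Visit 2 tracing precedes the first application. That is fair for withdrawals before Week 24. Read literally, however, a subject withdrawn on the Visit 10 tracing would miss Visit 11, the only planned off-drug ECG.

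On Visit 11 results, a reader might infer that anything read after discharge is lost. The documents do not support that. Sections 7.2.1 and 7.2.4 have no end date, Section 8.2.2 covers SAEs that occur in the period but are learned of later, and Section 8.2.1 sets a duty without barring later entries. What remains is a conflict of wording.

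**Conclusion.** The point holds for subjects who leave the study when drug stops. Their guaranteed off-drug reporting time is 0 days, against a planned 28 (20 to 36) for completers, and new AEs and SAEs after withdrawal are not reportable. The safety summaries therefore pool unequal windows. One missed event would shift a proportion by about 8 percentage points; how many subjects are affected cannot be known from the documents.

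Three broader conclusions are not supported:

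- Off-drug events in general do not fall outside the window, because completers' off-drug period lies inside it.
- No particular percentage of follow-up can be said to be lost, because any such figure rests on an assumed number of early leavers, each with no off-drug days.
- Permanent discontinuation under Section 8.2.4.2 cannot be equated with leaving the study, because that section does not say so.

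The effect on the treatment-emergent AE table is also uncertain, since Section 10.1 does not say whether off-drug events count. For Visit 11 results the finding is an inconsistency between Section 8.2.1 and Sections 7.2.1 and 7.2.4, not a demonstrated loss of data.

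**What to change.** In Section 8.1.3, keep Visit 11 as the end of the reporting period for completers. A 28-day minimum should not be imposed on them, since a compliant Visit 11 can fall 20 days after Visit 10. For subjects who leave early, end the period at the later of their last visit and 4 weeks after the last application, the interval already planned for completers. Collect AEs by telephone at that point if the subject does not attend, and cross-refer from Section 5.6.

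Separately, reword Section 8.2.1 so that the duty covers AEs with onset in the reporting period and clinically significant findings from samples or tracings taken in it, whenever they are read. That brings it into line with Sections 7.2.1 and 7.2.4.

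The cost is protocol wording and one extra contact for each early leaver. Those subjects' records stay open up to 4 weeks longer, and the AE count may rise slightly.
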